4.8. End of Study Definition

A patient is considered to have completed the study if he/she has completed 24 weeks of treatment including the Week 24 visit and the Follow-up Visit (for patients that complete the study through Week 24 but decide not to rollover to the OLE), or the last scheduled procedure shown in the Schedule of Assessments(SoA; Section 1.3). If the patient decides to continue into the OLE, subject must not participate in another interventional study until completing the ET/final follow-up visit (4 weeks after the last dose of study drug) according to the Schedule of Assessments OLE (Section 1.4 or 1.5).

The end of the study for assessment of the primary endpoint is defined as the date of the last visit of the last patient in the Main Study or last scheduled procedure in the Main Study shown in the SoA for the last patient in the study globally, regardless of duration of participation in the OLE.

5. STUDY POPULATION

5.1. Inclusion Criteria

Patients are eligible to be included in the study only if all the following criteria are met:

- 1. Male and female patients must be at least 18 years of age at the time of signing the informed consent.
 - a. Male patients and female partners of childbearing potential must agree to use contraception as detailed in a Section 5.4.1 to the protocol starting at Screening, during the treatment period, and for at least 100 days after the last dose of IP. Male patients must refrain from donating sperm during this period.
 - b. Female patients of childbearing potential must agree to use contraception as detailed in Section 5.4.1 starting at Screening, during the treatment period, and for at least 4 weeks after the last dose of IP.
- 2. Body mass index (BMI) $\geq 18 \text{ kg/m}^2 \text{ and } \leq 40 \text{ kg/m}^2$
- 3. Patients with symptomatic PAH belonging to one of the following 2018 Clinical Group 1 sub-types:
 - a. Idiopathic PAH
 - b. Heritable PAH
 - c. Drug- or toxin-induced
 - d. PAH associated with:
 - 1. Connective tissue disease
 - 2. Congenital systemic to pulmonary shunt (atrial septal defect, ventricular septal defect, patent ductus arteriosus) repaired at least one year prior to Screening
 - 3. Human immunodeficiency virus (HIV) infection if diagnosed with HIV, must have stable disease status defined as follows:
 - a. stable treatment with HIV medications for at least 8 weeks prior to Screening
 - b. no active opportunistic infection during the Screening Period
 - c. no hospitalizations due to HIV for at least 4 weeks prior to Screening
- 4. WHO FC II or III
- 5. Confirmed diagnosis of PAH and meet all the following hemodynamic criteria by means of a screening RHC completed prior to randomization:
 - a. mPAP of >20 mmHg
 - b. $PVR \ge 350 \text{ dyne-sec/cm}^5$
 - c. Pulmonary capillary wedge pressure (PCWP) or left ventricular end diastolic pressure (LVEDP) of ≤ 12 mmHg if PVR ≥ 350 and < 500 dyne•sec/cm⁵, or PCWP/LVEDP ≤ 15 mmHg if PVR ≥ 500 dyne•sec/cm⁵
- 6. 6MWD of 100 to 550 meters at Screening

- 7. Currently on a stable treatment regimen with one or more treatments approved for PAH. Stable therapy is defined as receiving the same medication(s) for ≥ 12 weeks prior to the screening RHC and at a stable dose level for each for ≥ 8 weeks prior to the screening RHC (see Protocol Section 6.6.2 for approved PAH medications). Any instances where doses of a medication have been missed prior to RHC must be discussed with the Medical Monitor prior to performing the RHC.
- 8. Meet all of the following criteria determined by pulmonary function tests completed no more than 24 weeks prior to Screening (performed with or without bronchodilation):
 - a. Forced expiratory volume in one second (FEV₁) \geq 60% of predicted normal, and
 - b. Total lung capacity (TLC) ≥ 70% of predicted normal or FVC ≥ 70% predicted if TLC is not available; For subjects with CTD associated PAH, if TLC is ≥ 60% of predicted but < 70% of predicted of if FVC ≥ 60% or predicted but < 70% of predicted, high resolution computed tomography [HRCT] obtained within 6 months of screening may be utilized to demonstrate limited interstitial lung disease
- 9. If participating in an exercise program for pulmonary rehabilitation, the program must have been initiated ≥ 12 weeks prior to Screening, and patient must agree to maintain the current level of rehabilitation for the first 24 weeks of receiving IP. If not participating in an exercise training program for pulmonary rehabilitation, patient must agree not to enroll in an exercise training program for pulmonary rehabilitation during the Screening Period and the first 24 weeks of receiving IP.
- 10. Willing and able to give written informed consent and to comply with the requirements of the study for its duration

5.2. Exclusion Criteria

Patients are excluded from the study if any of the following criteria are met:

1. Women of childbearing potential who are pregnant, planning to become pregnant, or lactating or female/male patients unwilling to use effective contraception as defined in Section 5.4.1

Medical Conditions

- 2. WHO pulmonary hypertension (PH) Group 1 PAH associated with portal hypertension or schistosomiasis; PH due to left heart disease (WHO PH Group 2), lung diseases and/or hypoxia (WHO PH Group 3), chronic thromboembolic PH (WHO PH Group 4), or PH with unclear multifactorial mechanisms (WHO PH Group 5)
- 3. PH associated with significant venous or capillary involvement (PCWP > 15 mmHg), pulmonary capillary hemangiomatosis, portal hypertension, or unrepaired congenital heart defects (CHD)
- 4. Three or more of the following risk factors for left ventricular disease:
 - a. BMI > 30 kg/m^2
 - b. Diagnosis of essential hypertension that is actively treated
 - c. Diabetes mellitus

d. History of significant coronary artery disease (e.g., chronic stable angina, history of coronary intervention within the last 3 months, or a stenosis > 70% at coronary angiography)

Protocol RVT-1201-2002

Effective: 19JAN2022

- e. Atrial fibrillation
- f. Left atrial volume index > 41 mL/m² [or left atrial diameter (LA) > 4 cm if LAVi unavailable]
- 5. Known genetic hypertrophic cardiomyopathy
- 6. Known cardiac sarcoidosis or amyloidosis
- 7. The patient has a history of, or currently has, a constrictive cardiomyopathy.
- 8. Known history of any left ventricular ejection fraction (LVEF) < 40% by echocardiogram within 3 years of randomization (**Note:** a transient decline in LVEF below 40% that occurred and recovered more than 6 months before the start of Screening and was associated with an acute intercurrent condition [e.g., atrial fibrillation] is allowed).
- 9. Hemodynamically significant valvular heart disease as determined by the Investigator, including:
 - a. greater than mild aortic and/or mitral stenosis and/or
 - b. severe mitral and/or aortic regurgitation (> Grade 3)
- 10. Severe arthritis, musculoskeletal problems, or morbid obesity that, in the opinion of the Investigator, is the cause of the patient's functional limitation and would affect the patient's ability to perform or complete the 6MWT.
- 11. Planned major surgery within the next 3 months, including lung transplantation, major abdominal or major intestinal surgery
- 12. End stage renal disease defined as receiving peritoneal dialysis, hemodialysis, or status after renal transplantation, or severe liver disease defined as Child-Pugh Class C, with or without cirrhosis
- 13. Known congenital LQTS or known family history of LQTS
- 14. Depression that is currently rated as severe (defined as a score of ≥ 16 on the QIDS-C and/or [HADS] Depression and/or Anxiety score ≥ 15), recent suicidal behavior (either preparatory acts/behavior, aborted attempt, interrupted attempt, or actual attempt in the past 3 months per the Screening C-SSRS), or active suicidal ideation with intent to act (defined as C-SSRS category score of 4 or 5 in the past month)
- 15. Patients with (during Screening):
 - a. Severe hypertension (SBP > 180 mmHg and/or Diastolic Blood Pressure [DBP] > 110 mmHg), and patients with severe hypotension (SBP < 90 mmHg and/or DBP < 50 mmHg)
 - b. Hypertension or hypotension considered not controlled in line with clinical standards
- 16. Clinically significant electrolyte abnormality (e.g., hypokalemia, hypomagnesemia, or hypocalcemia) in the judgement of the Investigator
- 17. Current or prior history within the last 5 years of neoplasm (except for treated basal cell or squamous small cell carcinoma of the skin with no evidence of recurrence)

18. Any concurrent clinically significant medical condition/disorder which in the Investigator's opinion would interfere with the patient's ability to comply with or complete the study or could affect the interpretation of the efficacy and safety variables.

Protocol RVT-1201-2002

Effective: 19JAN2022

Prior/Concomitant Therapy

- 19. Use of any of the following medications or supplements within 30 days prior to Screening:
 - monoamine oxidase inhibitors (MAOIs; Appendix 1)
 - 5-hydroxytryptophan (5-HTP) or L-tryptophan
 - telotristat ethyl
- 20. Patients currently taking one or more drugs known to prolong the QT interval and which are clearly associated with a known risk of Torsades de Pointe (see Appendix 1)

Diagnostic Assessments

- 21. Estimated glomerular filtration rate (eGFR) < 30 mL/min/1.73 m² at Screening
- 22. 12-Lead ECG results at Screening demonstrating QTcF interval > 450 ms for males or > 470 ms for females
- 23. Elevated ALT, AST, or TBL > 2X ULN
- 24. Any ECG or clinical laboratory abnormality which precludes safe participation in the study in the opinion of the Investigator

Lifestyle

- 25. History of active substance use disorder (including alcohol) within the past 2 years which, in the option of the Investigator, would limit the ability of the patient to provide adequate informed consent or to comply with study requirements
- 26. Use of any investigational drug within 30 days or 5 half-lives (whichever is longer) prior to Screening, or 90 days if an investigational drug for PAH, unless local health authority guidelines mandate a longer period, or in consultation with the medical monitor, will not interfere with the safety or efficacy of the study
- 27. Any history of hypersensitivity to rodatristat ethyl, any of its components, or any components in the placebo preparation (refer to current Rodatristat Ethyl IB).
- 28. Patient is deprived of their liberty by a judicial or administrative decision, or is receiving psychiatric care, and is admitted to a health or social institution
- 29. Patient is subject to legal protection or is unable to express consent

5.3. Other Eligibility Criteria Considerations

To determine patient eligibility at Screening, a single repeat of certain tests such as laboratory values, vital signs, or ECGs will be allowed.

To assess any potential impact on patient eligibility with regard to safety, the Investigator must refer to the rodatristat ethyl Investigator's Brochure for detailed information regarding warnings, precautions, contraindications, AEs, and other significant data pertaining to the IP being used in this study.

5.4. Lifestyle Considerations

5.4.1. Contraception

Female patients of childbearing potential who have a negative serum pregnancy test at Screening and a negative urine pregnancy test at the randomization visit must agree to use protocol-specified, highly effective contraception starting at Screening and for the duration of the study and for at least 4 weeks following the last dose of IP as follows:

- Use 2 methods of contraception in combination defined as a condom plus an approved method of effective contraception from the following list from the time of informed consent:
 - Combined (estrogen and progestogen-containing) hormonal contraception associated with inhibition of ovulation: oral, intravaginal, transdermal
 - Progestogen-only hormonal contraception: oral, injectable/implantable, intrauterine hormone-releasing system
 - Implantable intrauterine device
 - Bilateral tubal ligation performed less than 6 months prior to randomization
 - Partner with vasectomy
 - Sexual abstinence (refraining from heterosexual intercourse). If study patient chooses this option, site staff must follow-up to reconfirm throughout the study. If patient becomes sexually active, one of the above choices must be utilized and documented.

Female patients who are considered to have no childbearing potential (surgically sterile defined as bilateral tubal ligation, hysterectomy, bilateral salpingectomy, or bilateral oophorectomy) for at least 6 months prior to randomization may participate and are not required to use contraception as defined above.

Female patients who are postmenopausal and > 45 years of age with amenorrhea for at least 2 years may participate and are not required to use contraception as defined above.

Postmenopausal women with amenorrhea for less than 2 years must have documented follicle stimulating hormone (FSH) levels > 35 IU/mL and negative pregnancy test at the Screening Visit.

Male patients must agree to the following:

• Not to try to impregnate his partner from the Screening Visit until at least 100 days after the last dose of IP

Protocol RVT-1201-2002

Effective: 19JAN2022

- If his female partner is of childbearing potential, agree to use 2 methods of contraception in combination defined as a condom plus an approved method of effective contraception from the following list from the time of informed consent until at least 100 days after the last dose of IP:
 - Combined (estrogen and progestogen-containing) hormonal contraception associated with inhibition of ovulation: oral, intravaginal, transdermal
 - Progestogen-only hormonal contraception: oral, injectable/implantable, intrauterine hormone-releasing system
 - Implantable intrauterine device
 - Bilateral tubal ligation performed less than 6 months prior to randomization
 - Vasectomy
 - Sexual abstinence (refraining from heterosexual intercourse). If study patient chooses this option, site staff must follow-up to reconfirm throughout the study. If patient becomes sexually active, one of the above choices must be utilized and documented.
- Use condoms with partners that are pregnant until at least 100 days after the last dose of IP to ensure that the fetus is not exposed to the IP
- Not donate sperm for the duration of the study until at least 100 days after the last dose of IP

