7.6. Inclusion Criteria

- 1. Patient must have completed study assessments and procedures up to and including Week 24 in the Main Study.
- 2. Female patients of childbearing potential must have a negative serum or urine pregnancy test at the Week 24 visit and must agree to use contraception as detailed in Section 5.4.1 for at least 4 weeks after the last dose of IP. A female patient of childbearing potential is defined in Appendix 4.

3. Male patients are eligible to participate if they do not have a female partner who is pregnant or who intends to become pregnant during the OLE. Male patients and female partners must agree to use contraception as detailed in Section 5.4.1 of the protocol starting 4 weeks prior to the first dose of IP, during the treatment period, and for at least 100 days after the last dose of IP. Male patients must refrain from donating sperm during this period.

Protocol RVT-1201-2002

Effective: 19JAN2022

- 4. Patient must agree not to participate in a clinical study involving another investigational drug or device for PH/PAH while in the OLE (does not include registry or observational studies).
- 5. Patient must be competent to understand the information given in the IRB- or Independent Ethics Committee (IEC)-approved Informed Consent Form (ICF) and must sign the form prior to the initiation of any OLE procedures.

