9.2. Safety Assessments

9.2.1. Pregnancy Testing

Serum pregnancy tests will be obtained for all female patients of childbearing potential at Screening and every 4 weeks while on IP. Urine pregnancy tests will be obtained at all subsequent visits and must be confirmed negative at the Baseline Visit before randomization and IP dispensation. Additional pregnancy tests should be completed anytime menstruation is delayed and in women with infrequent or irregular menstrual cycles. A positive urine test will be confirmed by a serum test.

Serum pregnancy test and FSH levels will be obtained at the Screening Visit for any postmenopausal women with amenorrhea for < 2 years to confirm FSH level (must be > 35 IU/mL). If FSH value is confirmed as postmenopausal at Screening, no further pregnancy tests are required. If level does not confirm postmenopausal status, urine pregnancy tests will be required at all scheduled visits and patients must agree to use an approved method of highly effective contraception (refer to Section 5.4.1).

Planned time points for all safety assessments are provided in the SoA (Section 1.3, Section 1.4, and Section 1.5).

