APPENDIX 4. COLLECTION OF PREGNANCY INFORMATION

Protocol RVT-1201-2002

Effective: 19JAN2022

Definitions

Woman of childbearing potential

A woman is considered fertile following menarche and until becoming post-menopausal unless permanently sterile (see below).

If fertility is unclear (e.g., amenorrhea in adolescents or athletes) and a menstrual cycle cannot be confirmed before first dose of IP, additional evaluation should be considered.

Women in the following categories are not considered women of childbearing potential

- 1. Premenarchal
- 2. Premenopausal female with one of the following:
 - Documented hysterectomy
 - Documented bilateral salpingectomy
 - Documented bilateral oophorectomy
- 3. For individuals with permanent infertility due to an alternate medical cause other than the above, (e.g., Müllerian agenesis, androgen insensitivity), Investigator discretion should be applied to determining study entry.
- 4. **Note:** Documentation can come from the site personnel's review of the patient's medical records, medical examination, or medical history interview.
- 5. Postmenopausal female
 - A postmenopausal state is defined as no menses for 12 months without an alternative medical cause.
 - A high follicle stimulating hormone (FSH) level in the postmenopausal range may be used to confirm a postmenopausal state in women not using hormonal contraception or hormonal replacement therapy (HRT). However, in the absence of 12 months of amenorrhea, confirmation with more than one FSH measurement is required.
 - Females on HRT and whose menopausal status is in doubt will be required to use one of the non-estrogen hormonal highly effective contraception methods if they wish to continue their HRT during the study. Otherwise, they must discontinue their HRT to allow confirmation of postmenopausal status before study enrollment.

Collection of Pregnancy Information

Male patients with partners who become pregnant

- The Investigator will attempt to collect pregnancy information on any male patient's female partner who becomes pregnant while the male patient is in this study. This applies only to male patients who receive the investigational product.

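### Section 5.4.1 (with 9.2.1 and the schedule footnotes) and Appendix 4 define childbearing potential differently, and OLE inclusion criterion 2 relies on both

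*Protocol*

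**What the plan says.** **Section 5.4.1** exempts two groups of women from contraception.

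- The first is women who for at least 6 months before randomization have been "surgically sterile defined as bilateral tubal ligation, hysterectomy, bilateral salpingectomy, or bilateral oophorectomy". A more recent ligation, "Bilateral tubal ligation performed less than 6 months prior to randomization", appears only as one of the accepted contraceptive methods.
- The second is "Female patients who are postmenopausal and > 45 years of age with amenorrhea" of at least 2 years. Postmenopausal women with a shorter amenorrhea must have "documented follicle stimulating hormone (FSH) levels > 35 IU/mL and negative pregnancy test at the Screening Visit".

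**Section 9.2.1** repeats the FSH cut-off with the same number and unit. One confirming value at Screening ends pregnancy testing. Otherwise: "If level does not confirm postmenopausal status, urine pregnancy tests will be required at all scheduled visits", together with approved contraception.

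**The schedule footnotes** (Section 1.3 footnote 8; the pregnancy-test footnote in Section 1.4) waive pregnancy tests for surgically sterile women without defining the term. Footnote 8 places FSH at Screening only, for amenorrhea under 2 years.

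**Appendix 4** treats every woman as fertile from menarche to menopause unless permanently sterile. It then lists hysterectomy, bilateral salpingectomy and bilateral oophorectomy. On menopause: "A postmenopausal state is defined as no menses for 12 months without an alternative medical cause". FSH may be used for confirmation, but with less than 12 months of amenorrhea more than one measurement is required. It gives no age limit, FSH cut-off or unit.

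**Section 7.6, OLE inclusion criterion 2**, requires a negative pregnancy test at Week 24 and contraception according to Section 5.4.1 from women of childbearing potential, then adds: "A female patient of childbearing potential is defined in Appendix 4".

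**The concern.** Childbearing potential is the switch that turns pregnancy testing and contraception on or off. The protocol treats exposure in pregnancy as serious: Section 4.1 asks for two contraceptive methods and tests every 4 weeks, and Section 8.1 makes pregnancy a mandatory reason for discontinuation. In the OLE, where Appendix 4 is expressly invoked, dosing may run for 6.5 years.

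If two sections set the switch differently, about 68 sites must each choose. A site may leave untested a woman whom another section calls fertile, or impose duties that another section waives. A woman's status may also change between the Main Study and the OLE although nothing about her has changed.

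**Working it through.** There is no derived figure to reproduce, because no sample size, error rate or event count enters this point. The check sets the rules side by side and runs example patients through each.

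| Element | 5.4.1 / 9.2.1 / schedule footnotes | Appendix 4 |
|---|---|---|
| Tubal ligation, at least 6 months | Surgically sterile | Not listed |
| Amenorrhea needed | 2 years, or less with FSH above the cut-off | 12 months |
| Age limit | Over 45 for the 2-year route | None |
| FSH | One Screening value above a cut-off, if amenorrhea is under 2 years | Optional from 12 months; more than one measurement below 12 months; no cut-off |

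Five illustrative patients:

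| Patient | 5.4.1 / 9.2.1 | Appendix 4 |
|---|---|---|
| 1. Age 35, menstruating, tubal ligation 12 months ago | Exempt | Of childbearing potential |
| 2. Age 50, amenorrhea 18 months, FSH not above the cut-off | Tests and contraception | Not of childbearing potential |
| 3. Age 44, amenorrhea 30 months | Fits no exemption | Not of childbearing potential |
| 4. Age 50, amenorrhea 9 months, one FSH above the cut-off | No further tests | One FSH not sufficient |
| 5. Age 50, amenorrhea 30 months | Exempt | Not of childbearing potential |

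Four of the five differ. In patients 1 and 4, Section 5.4.1 with 9.2.1 is the looser rule. In patients 2 and 3, Appendix 4 is the looser one. Neither text is therefore simply a stricter version of the other.

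The instructions that act on these patients are as follows.

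1. *Tubal ligation.* Appendix 4 is a default with listed exceptions, so the omission has an effect. Through Section 7.6, patient 1 needs a negative test at OLE entry. The Section 1.4 footnote waives tests for the surgically sterile, and only Section 5.4.1 defines that term. After week 24 of the OLE, the Section 1.5 footnote ties 4-weekly tests to childbearing potential and carries no waiver for surgical sterility.
2. *Amenorrhea of 12 to 24 months.* Under Section 9.2.1, patient 2 is tested and uses contraception in the Main Study. At OLE entry, the definition in Appendix 4 places her outside criterion 2.
3. *Amenorrhea under 12 months.* Section 9.2.1 stops patient 4's tests after one value. Appendix 4 asks for a second measurement, and no later FSH is scheduled (Section 1.3 footnote 8; Section 9.2.5.5).

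**The case against.** **The Main Study can be run from Section 5.4.1 alone.** Sections 5.4.1 and 9.2.1 and footnote 8 agree on the 2-year limit and the Screening FSH, and Appendix 4 is titled as a procedure for collecting pregnancy information. This has some force for the second conflict, which bites mainly at OLE entry. But Appendix 4 also speaks of establishing fertility before the first dose and menopause before enrollment, so it does not confine itself to reporting.

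**The OLE also uses Section 5.4.1.** Criterion 2 cites it for contraception, and the Section 1.4 footnote keeps the waiver for surgical sterility. That is correct. A firm change in management at rollover is therefore not established. What is established is that the same criterion leads to two answers.

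**The 12-month definition could be read into the word postmenopausal in Section 9.2.1**, which would take patient 4 out of the single-FSH route. The protocol does not say so, and footnote 8 attaches FSH to amenorrhea under 2 years with no lower limit.

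**A reader might infer that the FSH sentence in Section 5.4.1 bars entry** to a woman whose value does not confirm menopause, while Section 9.2.1 admits her. The text does not compel this. The sentence follows two exemptions and can be read as a third, with Section 9.2.1 supplying the outcome when FSH does not confirm. The inclusion and exclusion criteria contain no FSH requirement. It is an ambiguity, not a contradiction.

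**A reader might also infer that the FSH unit is 1000-fold too large and that no woman could qualify.** The arithmetic is simple: 35 IU/mL × 1000 = 35,000 IU/L = 35,000 mIU/mL, which is 1000 times 35 mIU/mL. It shows an error only if mIU/mL or IU/L was intended. Sections 5.4.1 and 9.2.1 agree on IU/mL, Appendix 4 gives no unit, and no reference range or laboratory unit appears in the documents.

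**Conclusion.** The point holds as an internal inconsistency in the protocol. The two definitions differ on tubal ligation, length of amenorrhea, age and the number of FSH measurements, and OLE inclusion criterion 2 draws on both. Identifiable women receive opposite answers on testing or contraception.

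The size cannot be given as a count, because the documents do not say how many women fall into these groups. Four of five is a result for chosen examples, not a rate. It rests on reading the list in Appendix 4 as complete and the FSH route in Section 9.2.1 as having no lower limit of amenorrhea. No endpoint, analysis or statistical figure is affected.

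The conflict does not depend on the FSH unit, which is the same in both sections that state a cut-off. The unit remains a query only. This review takes no view on which definition or cut-off is right.

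**What to change.** Reconcile Section 5.4.1, Section 7.6 criterion 2, Section 9.2.1, the schedule footnotes (Sections 1.3 to 1.5) and Appendix 4 into one definition of childbearing potential, used in both the Main Study and the OLE. It should settle:

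- whether tubal ligation counts as sterility, and from when;
- the length of amenorrhea and any age limit;
- when FSH is needed and how many measurements, with the schedule matched to the answer;
- whether the FSH sentence in Section 5.4.1 is a condition for exemption or for entry.

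As a separate query, confirm with the central laboratory that the unit attached to the cut-off in Sections 5.4.1 and 9.2.1 is the one it reports.

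The cost is amendment wording. Pregnancy tests and a Screening FSH are already scheduled. Depending on the definition chosen, some women may need additional urine tests or a further FSH measurement.
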